## 6.1.5. Analysis Visit Windows

Statistical analyses will be based on scheduled visits as collected in the case report form (CRF) realigned on study days, which are defined based on the date of first emapalumab infusion (SD0) as follows:

Study Day = date of interest - date of first emapalumab infusion.

The following rules will be applied for MAS remission and glucocorticoid tapering.

- For the assessment of MAS remission and glucocorticoid tapering at Week 8, the SD56±5 days analysis period will be considered. Where several such observations occur in this time window, the one closest to SD56 will be selected. If there are 2 such observations that are equidistant from SD56, the observation that is after SD56 will be selected.
- For the assessment of time to MAS remission, see Section 6.1.7.

## **6.1.6.** Pooling of Sites

As relatively few patients are expected in the study, center will not be taken into account in the analyses.

### 6.1.7. Derived Variables

- Change from baseline = value at current time point value at baseline.
- Conversion factors: The following conversion factors will be used to convert days into months or years:
  - $\circ$  1 month = 30.4375 days
  - $\circ$  1 year = 365.25 days

AD-ST-33.04 Effective date: 30-Jun-2017

Version 2.0 | Date 29-Oct-2020 | AD-PR-109.01 Effective date: 26-Jun-2017

- Treatment-emergent AE (TEAE) = any adverse event with an onset date/time after the start of the first emapalumab administration.
- Infusion-related reactions (IRRs) = any TEAE that is reported to have occurred within 24 hours after start of infusion and assessed as related to study treatment by the Investigator, excluding the following system organ classes (SOCs): "Infections and infestations," "Congenital familial and genetic disorders," "Neoplasms benign, malignant and unspecified (incl. cysts and polyps)," "Product issues," "Social circumstances," and "Surgical and medical procedures."

If the onset time of the AE or the start time of the infusion is missing, then an AE with an onset date equal to an infusion date or infusion date + 1 will be considered for the assessment of IRRs.

- Infection: any TEAEs part of the SOC 'infection and infestation'.
- Duration of exposure (days) = date last study drug intake date first study drug intake + 1
- Study Day = date of interest date of first emapalumab infusion.

This SAP follows the protocol assumption that the day of the first infusion is SD0. Starting with 0, rather than with 1, can cause trouble for SDTM programming since it is not compliant with the SDTM Implementation Guide. SDTM data set will include two ways in counting the study day: starting with zero as in the protocol and starting with 1 as reccommended by the SDTM Inplementation Guide.

- Cumulative administered dose of emapalumab (mg/kg) = sum of administered emapalumab doses (mg/kg)
- Average administered dose of emapalumab (mg/kg) = (cumulative dose of emapalumab)/(number of doses)
- Equivalent dose of prednisone

The Systemic Glucocorticoids data are collected into two modules of the paper CRF:

- the 'Systemic Glucocorticoids from SD-3 until SD15" log
- the 'Concomitant Medication' log

For the analysis of systemic glucocorticoid dose tapering, conversion to prednisone-equivalent dose may be required, if different glucocorticoids have been administered. Furthermore, the glucocorticoid dose will be expressed as prednisone-equivalent mg/kg body weight/day.

AD-ST-33.04 Effective date: 30-Jun-2017

Version 2.0 | Date 29-Oct-2020 | AD-PR-109.01 Effective date: 26-Jun-2017

Page 21 of 51

Steps to calculate the prednisone equivalent dose (mg/kg/day):

- 1) Select systemic glucocorticoids where route is IV or oral from the 'Systemic glucocorticoids from SD-3 until SD15' form. Reported doses in the 'Systemic glucocorticoids from SD-3 unit SD15' form are daily doses and the number of doses per day is set to 1.
- 2) Select concomitant medications with ATC code H02B (Glucocorticoids) from the 'Concomitant medication' form with IV or oral route of administration. Calculate the frequency per day as follows (this list should not be seen as exhaustive):

Frequency	Description	Number of doses per day
OB, QD	Once a day	1
BID	Twice a day	2
TIB	Three times a day	3
QID	Four times a day	4
QW	Every week	1/7
2xW	Twice per week	2/7
3xW	Three times per week	3/7
NxW	N times per week	N/7
EVERY 2 WEEKS	Every 2 weeks	1/14
QM	Every month	1/30.4375
QAD	Every other day	0.5
Once	Single intake	1/(stop date – start date +1)
PRN	As needed	0
Other	Other	0
UNK	Unknown	0

AD-ST-33.04 Effective date: 30-Jun-2017

Version 2.0 | Date 29-Oct-2020 | AD-PR-109.01 Effective date: 26-Jun-2017

CI	Continuous infusion	0

Note: Administration of glucocorticoids with 'as needed', 'other', or 'unknown' frequency will not be included in the calculation of the equivalent dose.

- 3) If the dose unit is not mg, then the following conversion will be done: 1 g = 1000 mg, 1 mcg = 0.001 mg. IV and oral routes of administration are equivalent.
- 4) Select the weight in kg from the physical examination visit closest to the glucocorticoids administration date.
- 5) Calculate the equivalent dose of prednisone using the following formula:

Equivalent dose (mg/kg/day)= 
$$\frac{Conversion \ Factor * Dose(mg) * Number \ of \ doses \ per \ day}{Weight \ (kg)}$$

where the conversion factor is:

- 1 for prednisone
- 1.25 for methylprednisolone
- 1 for prednisolone
  - Glucocorticoids tapering = glucocorticoids permanently tapered
    - to the same (or lower) dose being administered before the occurrence of MAS (in patients already on treatment for sJIA/AOSD

or

• by at least 50% of the equivalent dose of prednisone administered at emapalumab treatment start (in those patients who present with MAS at sJIA/AOSD onset).

The daily equivalent dose of prednisone will be compared with the daily equivalent dose of prednisone at SD0.

AD-ST-33.04 Effective date: 30-Jun-2017

Version 2.0 | Date 29-Oct-2020 | AD-PR-109.01 Effective date: 26-Jun-2017

Page 23 of 51

If it is not possible to establish if a patient has been treated for sJIA/AOSD or not before study start for all patients, or if it is not possible to retrieve glucocorticoids dose administered before the occurrence of MAS for all patients who already are treated for sJIA/AOSD, the glucocorticoids tapering endpoint will be changed. In this case the endpoint will be: "glucocorticoids permanently tapered at any time during the study by at least 50% of the equivalent dose of prednisone administered at emapalumab treatment start (SD0).

If glucocorticoid dosing data are unavailable at a given time point, the assumption that dose has not been further tapered from the previous available observation will be made. Glucocorticoid doses will be calculated as (prednisone-equivalent) mg/kg/day.

- MAS remission = resolution of clinical signs and symptoms according to the Investigator (MAS clinical signs and symptoms score ≤ 1) AND normalization of laboratory parameter relevant to MAS as follows:
  - White blood cell count (WBC) and platelet count above the lower limit of normal (LLN)
  - Lactate dehydrogenase (LDH) below 1.5 upper limit of normal (ULN)
  - Alanine aminotransferase/aspartate aminotransferase (ALT/AST) below 1.5 ULN
  - Fibrogen higher than 100 mg/dL
  - Ferritin level decreased by at least 80% from values at screening or baseline (whichever is higher) or below 2000 ng/mL, whichever is lower

If one or more laboratory data are unavailable within the visit window, the LOCF approach will be used.

- MAS remission by week 8 = patients who meet MAS remission conditions in the period SD56  $\pm$  5 days regardless the time of first MAS remission or its duration.
- Survival:

Time to death = date of death - date of first emapalumab infusion + 1

Patients who survive to the end of the study will be censored at the date of last contact. In case in which a patient withdrew consent the censoring date will be the date of withdrawal of consent.

• Time to MAS remission:

AD-ST-33.04 Effective date: 30-Jun-2017

Version 2.0 | Date 29-Oct-2020 | AD-PR-109.01 Effective date: 26-Jun-2017

Page 24 of 51

date of first MAS remission – date of first emapalumab infusion + 1

Time to the first MAS remission will be calculated from the date of first emapalumab infusion until the date of first MAS remission. Patients who do not meet the criteria of MAS remission will be censored at the date of last contact.

The MAS remission evaluation is based on a combination of assessments, including Investigator assessment and laboratory findings. The latest date of assessments, within the visit window of  $\pm$  3 days around the planned day of the visit, will be used for the calculation of the time to MAS remission.

• Time to achievement of permanent glucocorticoids tapering:

date of glucocorticoids tapering – date of first emapalumab infusion + 1

Time to achievement of glucocorticoids tapering will be calculated from the date of first emapalumab infusion until the date in which the target level of glucocorticoid dose reduction is permanently achieved. Patients who do not meet the criteria of glucocorticoids tapering will be censored at the date of last contact.

• The total daily dose of anakinra, canakinumab, ciclosporin, etoposide, methotrexate, and tocilizumab will be calculated for each subject using the same unit of measurement provided in the concomitant medication log.

Total daily dose = dose \* Number of doses per day

Where the number of doses per day are derived using the same approach for the calculation of the equivalent dose of prednisone equivalent.

• Glucocorticoids tapering to  $\leq 1$  mg/kg/day of the equivalent dose of prednisone:

Achievement of permanent glucocorticoids tapering and last equivalent dose of prednisone is  $\leq 1$  mg/kg/day.

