## 5.2 DOSING REGIMEN

Emapalumab will be administered at the initial dose of 6 mg/kg by infusion over a period of one to two hours depending on the volume to infuse. Treatment will be continued at the dose of 3 mg/kg every 3 days until SD15, and twice-a-week thereafter for a total of 4 weeks (i.e. up to SD28).

Treatment may be shortened upon achievement of complete clinical response (i.e. MAS remission), however at least two infusions of emapalumab at the dose of 3 mg/kg have to be administered (i.e. after SD6).

In the absence of a trend of improvement in key MAS parameters (including, but not limited to ferritin, LDH, AST/ALT and PLT count) suggestive of lack of response, the emapalumab regimen may be adapted (the frequency between infusions shortened, the dose increased or the treatment prolonged beyond 4 weeks) upon assessment of a favorable benefit/risk profile in that individual patient.

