## 10.2 DESCRIPTION OF SAFETY PARAMETERS

Evaluation of emapalumab tolerability and safety will be based on the following parameters:

- Adverse events (AEs), with special attention being paid to potential infusion related reactions (IRRs), (i.e events occurring during or within 24 hours post infusion) and to the occurrence of infections, particularly with pathogens associated with lack of IFN $\gamma$  biological activity (due to emapalumab mode of action).
- Laboratory parameters, as described in [Section 8.4](#)
- Vital signs, as described in [Section 8.3.1](#)
- Physical examination with particular attention paid to evolution of signs and symptoms present at baseline, and to any emergent new signs or symptoms (see [Section 8.3.2](#) for more details).

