## 11. Changes from Planned Analysis

The Safety analysis set coincides with the All Treated Population and it is not listed in the analysis populations section. The EVAL Population has been added to check the robustness of the efficacy results. The Per-Protocol analysis set has been removed due to the small sample size and the introduction of the EVAL population.

Infusion-related reaction has been added in the safety endpoints (Section 2.2.1).

AD-ST-33.04 Effective date: 30-Jun-2017

Version 2.0 | Date 29-Oct-2020 | AD-PR-109.01 Effective date: 26-Jun-2017

The glucocorticoids tapering endpoint has been modified when it is not possible to establish whether a patient have been treated for sJIA/AOSD or not before study start for all patients or when it is not possible to retrieve glucocorticoids dose administered before the occurrence of MAS for all patients who already are treated for sJIA/AOSD. In this case the endpoint is "Number of patients for whom, at any time during the study, glucocorticoids can be tapered by 50% (or more) of the dose administered at emapalumab treatment start.

IL-10, sCD163, TNFa and IL-18 may be analysed and/or reported separately.

The following have been added:

- safety patient profile reports (Section 12.1)
- descriptive summaries of neutralizing antibody in case of positive ADA results (Section 9.5.3)
- Number and percentage of patients who tapered steroids to  $\leq 1 \text{mg/kg/day}$  of the equivalent dose of prednisone (Section 6.1.7)

No other changes from the analyses specified in the protocol are planned.

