Version 2.0 | Date 22-Jul-2021 | AD-PR-109.02 Effective date: 17-Aug-2020 Page 6 of 18

Section 6.1.7 - Derived variables/ IRR with missing start date	"If the onset time of the AE or the start time of the infusion is missing, then an AE with an onset date equal to an infusion date or infusion date + 1 will be considered for the assessment of IRRs."	Describe how completely missing AE start date will be imputed for an IRR assessment.  Corrected to "If the onset time of the AE or the start time of the infusion is missing, then an AE with an onset date equal to an infusion date or infusion date + 1 will be considered for the assessment of IRRs. If the onset date of the AE is completely missing, the AE will be considered as IRR (most conservative approach)."
Section 6.1.7 - Derived variables/ Infection definition	"Infection = any TEAEs part of the SOC 'infection and infestation'"	Infection definition updated to a broader search strategy for all potential infections with emapalumab use.  /  Updated to Infection = All AEs in the SOC "Infections and infestations" or in the HLGT "Microbiology and serology investigations".
Section 6.1.7 - Derived variables/ Selection of systemic glucocorticoid dose	"Select concomitant medications with ATC code H02B"	Selection should be applied on ATC code H02AB. The ATC level 4 H02AB correctly and specifically corresponds to GLUCOCORTICOIDS, whereas in the SAP version 2.0, selection by code H02B is an error, as this code does not include plain glucocorticoid products, but only combinations (CORTICOSTEROIDS FOR SYSTEMIC USE, COMBINATIONS).

[figure not shown]
 Version 2.0
 Date 22-Jul-2021
 AD-PR-109.02
 Effective date: 17-Aug-2020
 Page 7 of 18

		1
		Corrected to "Select medications with ATC Level 4 code H02AB"
Section 6.1.7 – Derived variables/ Steps to calculate the prednisone	"4) Select the weight in kg from the physical examination visit closest to the glucocorticoids administration date."	Further clarification on which assessment should be selected if observations are equidistant and prior to first treatment administration.
equivalent dose (mg/kg/day)		Under the Steps to calculate the prednisone equivalent dose (mg/kg/day), corrected to:

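### The SAP's infusion-related reaction definition is narrower than the protocol's timing-only description, and no planned table shows time-qualifying events regardless of causality

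*SAP*

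**What the plan says.** Protocol 10.2 (Description of Safety Parameters) singles out potential IRRs for special attention and explains the term by timing only: "events occurring during or within 24 hours post infusion". It sets no causality condition and excludes no organ class.

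SAP 6.1.7 (Derived Variables) defines an IRR as a treatment-emergent adverse event reported "within 24 hours after start of infusion and assessed as related to study treatment by the Investigator". It then removes six system organ classes: infections, congenital disorders, neoplasms, product issues, social circumstances, and surgical and medical procedures. If an onset time or infusion start time is missing, an event with "an onset date equal to an infusion date or infusion date + 1 will be considered for the assessment of IRRs". The SAP errata adds a rule for a wholly missing onset date and leaves the 24-hour window, its anchor and the relatedness condition as they were.

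SAP 9.1.3 and Table 14.3.2.3 tabulate IRRs under this definition. SAP section 11 (Changes from Planned Analysis) records that IRR was added to the safety endpoints in 2.2.1, although 2.2.1 does not list it. Section 11 does not mention that the definition differs from protocol 10.2, and it closes with "No other changes from the analyses specified in the protocol are planned".

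**The concern.** The SAP departs from the protocol's description in three ways, all in the same direction: the clock starts at the beginning of the infusion rather than running on from its end, investigator relatedness is required, and six organ classes are removed.

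The relatedness condition matters most. Protocol 10.3.1 makes causality a yes/no judgement and says that a negative answer usually means another possible cause was found. In these patients another cause is nearly always at hand. Protocol 8.3.3 lists fever and skin rash among the signs of macrophage activation syndrome (MAS), and protocol 10.5.2.2 reports rash as the infusion finding already seen with this drug. The study is open-label with no control arm, so nothing shows the background rate of such events.

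Infections, the other category that protocol 10.2 singles out, are counted in the SAP without a causality condition, and the errata broadened that definition.

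What is at stake is how the IRR table reads. A reader who knows protocol 10.2 could take it to cover every event in the post-infusion day, when it covers only those attributed to the drug.

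**Working it through.** **Inputs.** Infusion duration T is 1 to 2 hours: protocol 5.2 gives the drug "by infusion over a period of one to two hours depending on the volume to infuse". The protocol window is the infusion plus 24 hours after it (10.2). The SAP window is 24 hours from the start (6.1.7). The planned sample is about 12 patients (SAP 3.2). Neither document states an expected IRR rate or a relatedness rate, so there is no plan figure to reproduce.

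**Anchor.** Measured from the start of infusion, the protocol window is T + 24 hours and the SAP window is 24 hours. The time lost is T, and its share of the protocol window is T / (T + 24).

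| T | Protocol window | SAP window | Lost | Share lost | SAP cover after end of infusion |
|---|---|---|---|---|---|
| 1 h | 25 h | 24 h | 1 h | 1/25 = 4.0% | 23 h |
| 2 h | 26 h | 24 h | 2 h | 2/26 = 7.7% | 22 h |

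Protocol 11.1.3 allows an infusion to be slowed or interrupted when vital signs change. T is then longer and more of the window is lost, at infusions where a reaction may be suspected.

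**Set relation.** An infusion cannot end before it starts, so any onset within 24 hours of the start also lies within the infusion or the 24 hours after it. The relatedness condition and the organ-class exclusions only remove events. With complete dates, times and causality, every SAP IRR is therefore a protocol potential IRR, and the SAP count is equal or lower.

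**Missing data.** Three rules work the other way:
- Date matching on the infusion day or the next day can admit onsets more than 24 hours after the start (SAP 6.1.7).
- The errata rule reads "If the onset date of the AE is completely missing, the AE will be considered as IRR (most conservative approach".
- A missing relationship is taken as related in the adverse event summaries (SAP 9.1).

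None of these affects an event with complete data.

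**Relatedness filter.** Its size cannot be derived. As an illustration by assumption, let q be the proportion of patients with a time-qualifying event and r the proportion of those with one called related. Expected patients are 12q on timing alone and 12qr with the filter.

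| q | Timing only, 12q | With filter, r = 0.25 | r = 0.50 | r = 0.75 |
|---|---|---|---|---|
| 0.10 | 1.2 | 0.3 | 0.6 | 0.9 |
| 0.30 | 3.6 | 0.9 | 1.8 | 2.7 |
| 0.50 | 6.0 | 1.5 | 3.0 | 4.5 |

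If r is 1 there is no loss. For scale, one patient is 1/12 = 8.3 percentage points. The exact 95% intervals are 0% to 26.5% for 0/12 and 0.2% to 38.5% for 1/12.

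**Other outputs.** SAP 9.1 tabulates all treatment-emergent events by term, severity and relationship. None of those tables is restricted by time from infusion. The count on timing alone could be rebuilt only by hand from the adverse event and infusion listings.

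**The case against.** The strongest reply is that the two documents do different jobs. Protocol 10.2 is a surveillance prompt about potential reactions. Protocol 7.3 lists no IRR endpoint and protocol 12.3.2 plans no IRR table. A wide timing net for vigilance and a related-only definition for reporting can coexist, and requiring relatedness for something called an infusion-related reaction is defensible. A timing-only rule would also pick up much background illness: ten infusions with 24-hour windows cover 240 of the 672 hours in 28 days, about 36%. The excluded events remain in the general tables and listings, and about 12 patients can be read line by line. The anchor effect is small.

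All of that stands. It rules out some stronger readings:
- A reader might infer that the reported rate is systematically below a protocol-specified rate. The protocol specifies no IRR rate, and the difference could be zero.
- A reader might infer from the SAP's document history, where suspected and confirmed IRRs were combined, that the definition was narrowed at that step. The log describes superseded text, the version 1.0 definitions are not available, and combining two categories does not show narrowing.
- A reader might infer that events judged unrelated vanish from safety reporting. They drop out of one table and its listing only.

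The reply does not supply a table of time-qualifying events regardless of causality, and it does not explain why section 11 leaves the difference from protocol 10.2 unstated.

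**Conclusion.** The point holds as a gap in safety reporting and an undeclared difference between the documents. It does not make the related-only row wrong. With complete data the SAP's IRR count is equal to or lower than the number of potential IRRs under protocol 10.2. The anchor accounts for 1 to 2 hours per infusion (4.0% to 7.7% of the protocol window), assuming infusions run to the stated duration. The relatedness filter is probably the larger effect; that is a judgement from the design and the disease, since no document gives a rate. The organ-class exclusions narrow the set further by an unknown amount. No efficacy result depends on this, but the reported IRR count can change, and at this sample size one patient is visible.

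**What to change.** 1. In SAP 6.1.7, run the window from the start of infusion to 24 hours after the end of infusion. Protocol 5.4.4.2 already requires both times to be recorded. Extend the missing-time rule to a missing end time. The existing date match still covers the window for any infusion that ends on the day it started.
2. In Table 14.3.2.3, show (a) all treatment-emergent events in that window regardless of causality and (b) the investigator-related subset as the IRR row.
3. State whether the six organ-class exclusions apply to both rows, and identify them as a departure from protocol 10.2.
4. Declare the definition in SAP section 11, and list IRR in section 2.2.1, where section 11 says it was added.
5. If the database is already locked, label the added row post hoc.

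The cost is wording and one table row. That row will contain some background illness and may look less favourable, so a footnote should say that it is defined by timing alone.

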 AD-PR-109.02
 Effective date: 17-Aug-2020
 Page 9 of 18

	T	<del>-</del>
Section 6.1.7 – Derived variables/ Definition of Biologics	No specification of biologics concomitant used is specified in the SAP version 2.0.	Concomitant use of relevant biologics will be also summarized per section 9.6 however no specification was provided under section 6.1.7.  /  Specifications added: "Relevant concomitant biologics medications will be defined as medications from ATC 4 levels L04AB, L04AC."
Section 6.1.8 - Data Adjustments/Han dling/Convention s/ Handling partial or missing start/stop dates for equivalent daily dose of prednisone, and daily total doses of anakinra, canakinumab, ciclosporin, etoposide, methotrexate, and tocilizumab	No details regarding how to handle partial or missing start/stop dates for equivalent daily dose of prednisone, and daily total doses of anakinra, canakinumab, ciclosporin, etoposide, methotrexate, and tocilizumab	To add detail on how to handle partial or missing start/stop dates for equivalent daily dose of prednisone, and daily total doses of anakinra, canakinumab, ciclosporin, etoposide, methotrexate, and tocilizumab.  /  Imputation of partial/missing medication start or stop dates for equivalent daily dose of prednisone and daily total doses of anakinra, canakinumab, ciclosporin, etoposide, methotrexate, and tocilizumab: -Partial medication end date  • If only month and year are available, medication end date will be imputed to the last day of the corresponding month  • If only year is available, medication end date will be imputed to the 31st of December of the corresponding year -Partial medication start date  • If only month and year are available, medication start date  • If only month and year are available, medication start date

[figure not shown]
Version 2.0 | Date 22-Jul-2021 | AD-PR-109.02 Effective date: 17-Aug-2020 Page 10 of 18

date will be imputed to the
1st day of the
corresponding month
• If only year is available,
medication start date will
be imputed to the 1st of
January of the
corresponding year.
-Medication start and end dates are
both missing, then the record of the
medication will not be considered
(i.e. no derivation of equivalent
dose of prednisone or daily dose of
anakinra,).
-Medication end date is missing
(and medication start date not
missing)
• When medication end date
is missing and "Ongoing" is not ticked
If medication start
date < Study day -
180, then this
record will not be
considered (i.e. no

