derivation of
equivalent dose of
prednisone or daily
dose of anakinra,
).
■ If Study day -180 ≤
medication start
date < Study day 0,
then medication
end date is set to
medication start
date.
• If medication start
$date \ge Study day 0,$
then medication
end date is set to
end of study date of

[figure not shown]
Version 2.0 | Date 22-Jul-2021 | AD-PR-109.02 Effective date: 17-Aug-2020 Page 11 of 18

		the corresponding patient.  • When "Ongoing" is ticked, then medication end date is set to end of study date of the corresponding patient unless medication start date > end of study date then set to medication start date of the corresponding patient.  -Medication start date is missing (and Medication end date is not missing)  • If medication end date < Study day -180, then this record will not be considered (i.e. no derivation of equivalent dose of prednisone or daily dose of anakinra,).  • If medication end date ≥ Study day -180, then the medication start date will be set to the medication end date.  Note: medication end date if available should have priority over
		the ongoing flag.
Section 6.1.8 - Data Adjustments/ Handling/ Conventions/ Handling < LLOQ, > ULOQ	No details regarding how the laboratory data below or above the limit of quantification will be handled.	Imputation rules to be applied to shift table when laboratory data below or above the limit of quantification. Laboratory listings will present data as collected.  / Imputation rules added: "Values
		below the lower limit of quantitation (i.e. < LLOQ) for individual values will be imputed to zeros when summarizing for

[figure not shown]
 Version 2.0
 Date 22-Jul-2021
 AD-PR-109.02
 Effective date: 17-Aug-2020
 Page 12 of 18

		descriptive statistics. Values above the upper limit of quantitation (i.e. > ULOQ) for individual values will be imputed to ULOQ values when summarizing for descriptive statistics."
Section 7.2 – Protocol Deviations / Correction	"Relevant protocol deviations categorized as major and minor will be tabulated in a summary table. Individual major and minor protocol deviations will be listed by patient."	Change in category terminology (applicable to the classification of deviations from a study conduct perspective) to align with references in regulations ICH E3 Q&A R1 and ICH GCP E6 R2.

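### A one-off steroid record coded 'Once' whose stop date is missing, partial or ticked ongoing can be spread over later days, which understates its own day and adds a phantom dose to the taper derivation

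*SAP*

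**What the plan says.** SAP 6.1.7 derives a daily prednisone-equivalent dose as conversion factor × dose × number of doses per day ÷ weight. Entries on the dedicated SD-3 to SD15 steroid log count as daily doses with a frequency of 1. Entries on the concomitant medication log take their frequency from a table, where 'Once', described as a single intake, is given "1/(stop date – start date +1" (bracket closed).

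The errata entry for 6.1.8 completes dates for this same derivation. Its branches depend on the start date and the 'Ongoing' box, never on frequency:

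- Stop missing, not ongoing, start on or after SD0: the "end date is set to end of study date of" the patient concerned.
- Stop missing, not ongoing, start from SD-180 to before SD0: stop is set to start.
- Stop missing and ongoing: when the box "is ticked, then medication end date is set to end of study date of the corresponding patient", unless the start is later than the end of study.
- Stop partial: "If only month and year are available, medication end date will be imputed to the last day of the corresponding month"; with only a year, 31 December.

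For anakinra, canakinumab, ciclosporin, etoposide, methotrexate and tocilizumab, SAP 6.1.7 carries the frequency table over: "Where the number of doses per day are derived using the same approach for the calculation of the equivalent dose of prednisone equivalent".

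The daily equivalent dose is compared with SD0 to define permanent tapering and its date. The last daily dose enters the ≤1 mg/kg/day flag. SAP 8.1 reports the two proportions with exact confidence intervals and the time by Kaplan-Meier.

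**The concern.** Running an undated stop to the end of study is a reasonable assumption for a drug that continues. It contradicts the meaning of a single intake. When the two rules meet, the total dose is preserved but moved off the day it was given and onto a run of later days. That makes two errors: the true day is understated, and each following day carries a dose the patient did not receive.

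The errata is also not consistent with itself. An identical record starting just before SD0, with stop wholly missing and not ongoing, collapses to one day, which is right. From SD0 onwards it does not.

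At stake are the tapering proportion, the time to permanent tapering, the ≤1 mg/kg/day proportion and the individual patient profiles, in a study of about 12 patients.

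**Working it through.** The documents give no worked figure for this derivation, so there is nothing to reproduce. The check applies the SAP formula directly.

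**Inputs from the documents.** Last visit normally SD56 (Protocol 3.4). Methylprednisolone factor 1.25 (SAP 6.1.7). Background at SD0 of at least 2 mg/kg/day (Protocol 6.1). Illustrative pulse of 30 mg/kg: methylprednisolone in the Protocol synopsis, so 1.25 × 30 = 37.5 mg/kg prednisone-equivalent; Protocol 4.1.1 words the same pulse as PDN, which gives 30.

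**Assumptions not in the documents.** SD0 dose exactly 2 mg/kg/day, so the 50% threshold is 1.0. Background 2 mg/kg/day to SD9, 0.8 to SD15, then 0.5 (or 0). Same-day records summed.

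**Step 1: the spread dose.** Days = 56 − start + 1; daily dose = pulse ÷ days.

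| Start | Days | 37.5 mg/kg becomes | 30 mg/kg becomes |
|---|---|---|---|
| SD16 | 41 | 0.91 per day | 0.73 |
| SD20 | 37 | 1.01 | 0.81 |
| SD30 | 27 | 1.39 | 1.11 |
| SD42 | 15 | 2.50 | 2.00 |
| SD49 | 8 | 4.69 | 3.75 |

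Starts up to SD43 are spread over at least 14 days (56 − 43 + 1 = 14). A start on SD56 spans one day and nothing changes.

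**Step 2: a large pulse (37.5 mg/kg on SD30, background 0.5).** Placed on its own day, the dose is below threshold from SD31 onwards: permanent taper yes, time 31 − 0 + 1 = 32 days, last dose 0.5, ≤1 mg/kg/day flag yes. Under the rules as written, SD30 to SD56 carry 0.5 + 1.39 = 1.89: permanent taper no, time censored, ≤1 flag no. With background 0.5, both flags change for each start tested from SD16 to SD49. With background 0, they change from SD20 onwards, where the spread dose alone exceeds 1.0; at SD16 it is 0.915, the flags hold, and the time becomes 11 days instead of 18.

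**Step 3: a smaller pulse (10 mg/kg on SD30, background 0.5).** Spread dose 10/27 = 0.37; total 0.87, under the threshold. The re-escalation vanishes and the taper dates from SD10: time 11 days instead of 32.

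**Step 4: sensitivity to the SD0 dose.** For the SD16 pulse over background 0.5 the total is 0.5 + 0.915 = 1.415. The 50% target is missed only if the SD0 dose is below 2 × 1.415 = 2.83 mg/kg/day. The ≤1 flag fails whatever the SD0 dose.

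**Step 5: direction.** For starts after SD0, spreading can only raise later days, so the yes/no flags move from yes to no. Time to taper can err either way. A concomitant-log 'Once' record starting on SD0 itself would also alter the SD0 comparator (37.5/57 = 0.66 per day).

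**The case against.** The case for leaving this alone is substantial.

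- **It needs a chain of conditions:** a concomitant-log record, coded 'Once', with a stop date that is missing, partial or ticked ongoing. The documents show no such record. Protocol 15.1 forbids blank CRF fields and Protocol 13.2 provides for frequent monitoring and query resolution. This lowers the likelihood; it does not correct the rule.
- **The early period is largely protected.** The SD-3 to SD15 log is exempt, and starts from SD-180 to before SD0 with stop wholly missing and not ongoing become one-day records. Exposure is therefore mainly after SD15. The protection before SD0 is not complete: partial and ongoing stops widen the span whatever the start date.
- **The example pulse is borrowed.** It comes from the eligibility text, where it is given on three consecutive days before entry. Protocol 6.1 describes re-escalation as a higher dose that is maintained, not a lone intake. That is fair, so the figures show scale only.
- **The flag changes rest on assumptions:** the dose path, the summing of same-day records, and a patient judged against the SD0 dose and not a pre-MAS dose. This stands, and is why a range is shown.
- **A flat dose running to SD56 should be noticed.** Calculated variables are listed (SAP 14.2) and the prednisone-equivalent is plotted per patient (SAP 12.1). All endpoints are exploratory (SAP 4.1). Detection on review is plausible, but the plan gives the reviewer no rule for correcting what is found.

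A reader might also infer that the six immunosuppressants widen the damage. They share the frequency table, but none of their daily doses defines an efficacy endpoint in SAP 8.1, and Protocol 6.3 restricts several of them once emapalumab starts.

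**Conclusion.** The rule is wrong as written for a narrow class of records. SAP 6.1.7 and the errata entry for 6.1.8, read together, convert a single dose into a daily dose up to the imputed stop date, and nothing exempts single intakes. For a 37.5 mg/kg dose on SD16 with no stop date, the derived value is 0.91 mg/kg/day for 41 days, about 41-fold too low on the day given and too high on every later day.

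Whether an endpoint changes depends on the pulse size, its day, the background dose and the SD0 dose. Under the assumed paths the outcomes run from a taper time that is too early to both flags lost and the time censored. One patient in 12 is 1/12 = 8.3 percentage points; that is the unit of the proportion, not an estimate of bias.

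A reader might go further and conclude that pulses are hidden and the taper results corrupted. The documents do not support that, because they do not give the number of affected records. The point should be put right because the correction is cheap, with the size of any actual effect left open.

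**What to change.** Add one line to the errata entry for 6.1.8: for frequency 'Once', before any other date imputation, a missing, partial or ongoing stop date is set to the start date, so that the record contributes one dose on that day and none on any other. With stop equal to start, the existing divisor already gives 1, so the frequency table needs no change.

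Use the same derivation for the other total daily doses in SAP 6.1.7, to keep listings and profiles consistent. Before lock, list all 'Once' records on the concomitant log whose stop date is missing, partial or ongoing; that count settles whether the issue touched any patient.

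The cost is one errata line, one programming condition and a short listing. No new data are needed, and records already dated with stop equal to start are unaffected. The errata already amends this section and is to be filed before database lock.
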